### 7.5.2 *Adverse Events*

Treatment-emergent adverse events are defined as those AEs with onset after the first dose of either study drug or existing events that worsened after the first dose during the study. Treatment-emergent AEs will be summarized for all subjects combined. Events reported with a partial onset date (eg, month and year are reported but the day is missing) will be considered to be treatment-emergent if it cannot be confirmed that the event onset was prior to the first dose of either study drug based on the available date entries.

Verbatim terms on case report forms will be mapped to preferred terms and system organ classes using the Medical Dictionary for Regulatory Activities (MedDRA, version 23.0). Adverse events will be graded according to the National Cancer Institute Common Terminology Criteria for Adverse Events (NCI-CTCAE).

Summaries that are displayed by system organ class and preferred terms will be ordered by descending incidence of system organ class and preferred term within each system organ class. Summaries displayed by preferred term only will be ordered by descending incidence of preferred term. Summaries of the following types will be presented:

- Overall summary of number of unique TEAEs and treatment-emergent SAEs and subject incidence of TEAEs meeting various criteria;
- Subject incidence of TEAEs by MedDRA system organ class and preferred term;
- Subject incidence of the most frequently-occurring TEAEs (ie, TEAEs occurring in  $\geq 10\%$  of the All Treated Population) by MedDRA preferred term;
- Subject incidence of TEAEs by NCI-CTCAE grade, MedDRA system organ class, and preferred term;
- Subject incidence of TEAEs related to each study drug and both study drugs by NCI-CTCAE grade, MedDRA system organ class, and preferred term;
- Subject incidence of TEAEs by relationship to each study drug, MedDRA system organ class, and preferred term;
- Subject incidence of the most frequently-occurring TEAEs related to each study drug and both study drugs (ie, related TEAEs occurring in  $\geq 10\%$  of the All Treated Population) by MedDRA preferred term;
- Subject incidence of TEAEs with NCI-CTCAE grade  $\geq 3$  and related to each study drug and both study drugs by MedDRA system organ class and preferred term;

- Subject incidence of treatment-emergent SAEs by MedDRA system organ class and preferred term;
- Subject incidence of treatment-emergent SAEs by NCI-CTCAE grade, MedDRA system organ class, and preferred term;
- Subject incidence of treatment-emergent SAEs related to each study drug and both study drugs by NCI-CTCAE grade, MedDRA system organ class, and preferred term; and
- Subject incidence of TEAEs leading to withdrawal, delay, reduction, or interruption of each study drug and both study drugs by MedDRA system organ class and preferred term.

At each level of summarization (eg, any AE, system organ class, and preferred term), subjects experiencing more than one TEAE will be counted only once. In the summary of TEAEs by severity grade, subjects will be counted once at the highest severity reported at each level of summarization; in the summary of TEAEs by relationship, subjects will be counted once at the closest relationship to study drug.

Adverse event data will be presented in data listings by subject and event.

### **7.5.3 *Deaths, Other Serious Adverse Events, and Other Significant Adverse Events***

All deaths during the study, including the post-treatment follow-up period, will be listed by subject, to include the primary cause of death. Serious AEs and other significant AEs, including those that led to withdrawal, delay, interruption, or reduction of each study drug, will be provided in separate subject data listings.

### **7.5.4 *Clinical Laboratory Evaluation***

All descriptive summaries of laboratory results will be based on data collected on the eCRF and presented in Système International (SI) units, as suggested by the Center for Biologics Evaluation and Research and the Center for Drug Evaluation and Research *Position on Use of SI Units for Lab Tests* (Oct 2013). All data will be included in by-subject data listings. Laboratory measurements identified as abnormal (ie, outside the normal range) will also be listed separately by subject, laboratory test, and unit. In addition, normal ranges provided by each site will be presented in a separate listing.

Clinical laboratory measurements, including serum chemistry and hematology, will be summarized for all subjects combined. Descriptive statistics will be presented for observed values and changes from baseline at each visit where parameters were scheduled to be collected per the clinical study protocol.

Where applicable, laboratory results will be classified as “low,” “normal,” or “high” with respect to the parameter-specific reference ranges (ie, below the lower limit of the normal range, within the normal range, or above the upper limit of the normal range). Three-by-

three contingency tables will be presented for each laboratory parameter to summarize the shift from the baseline category to the worst post-baseline measurement, defined as the value numerically farthest outside of the normal range across all post-baseline visits through the end of the study.

Summary results will include the count and percentage of subjects within each shift category.

Where applicable, hematology, chemistry, and coagulation results for select parameters will be assigned a toxicity grade based on the NCI-CTCAE. If the quantitative criteria for grading are equivalent for two grades and the differentiation is described by clinical interventions, the clinical intervention component will not be considered and the highest NCI-CTCAE grade will be assigned. Similarly, death related to AE (ie, Grade 5) cannot be determined with available laboratory-based data collection and, thus, will not be summarized as a category. Laboratory parameters that include multiple sets of criteria for each direction (eg, separate criteria for potassium measures to assess hyperkalemia and hypokalemia) will be summarized separately to reflect each set of criteria.

A five-by-five contingency table will be presented for lab tests where toxicity grading can be applied, to summarize the shift from the baseline grade to the worst post-baseline grade. Grades will be presented as none (Grade 0; ie, measurements did not meet any NCI-CTCAE criteria for Grades 1 through 4), mild (Grade 1), moderate (Grade 2), severe (Grade 3), or life-threatening (Grade 4). Summary results will include the count and percentage of subjects within each shift category.

A separate table will be provided to assess the potential for drug-induced liver injury. Laboratory values consistent with Hy's Law criteria will be presented. Summary results will include the count and percentage of subjects within each shift category.

## **7.5.5 Vital Signs, Physical Findings, and Other Observations Related to Safety**

### **7.5.5.1 Vital Signs**

Vital sign parameter measurements will be summarized for all subjects combined. Descriptive statistics will be presented for observed values and changes from baseline at each visit where parameters were scheduled to be collected.

### **7.5.5.2 12-Lead Electrocardiogram**

Twelve-lead ECG interval parameters will be summarized for all subjects combined. Descriptive statistics will be presented for observed values and changes from baseline at each visit where parameters were scheduled to be collected. Measurements will be taken in triplicate, and the average measurement will be summarized.

Twelve-lead ECG will be classified by the investigator as "normal," "abnormal, not clinically significant," or "abnormal, clinically significant." Three-by-three contingency tables will be presented to summarize the shift from the baseline category to the worst

post-baseline value. Summary results will include the count and percentage of subjects within each shift category.

Prolonged QTcF intervals will be summarized as QTcF measurements (msec) that are > 450, > 480, and > 500 at each visit where ECG is routinely collected per the clinical study protocol. Change from baseline categories will also be summarized for measurements that represent an average change > 30 or > 60 relative to the average baseline value. Summary results will include the percentage of subjects within each category.

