**Table 2-2 12-lead ECG Collection Timepoints**

Triplicate ECGs should be completed at each timepoint, and the mean QTcF values should be calculated.

Cycle	Day	Time
Screening	Anytime during the screening period	
1	1	Pre-dose and within 30 minutes after start of ADU-S100 injection
1	8	Pre-dose and within 30 minutes after start of ADU-S100 injection
2	1	Pre-dose
3	1	Pre-dose
EOT	EOT	
Unscheduled	Anytime if clinically indicated	

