### 10.3.4 Electrocardiogram

At screening and during the study ([Table 2-2](#)), triplicate ECG assessments will be performed with local 12-lead ECG equipment according to standard procedures to determine the corrected QT interval calculated by Fridericia formula (QTcF). At screening, the average value of the triplicate will be utilized for enrollment into the study.

The triplicates should be performed no less than 3 minutes apart, and within approximately 30 minutes of the initial ECG to determine the mean QTcF interval. All 12-lead ECGs should be performed after the subject has rested in a recumbent or semi-recumbent position for  $\geq 5$  minutes. Additional ECGs may also be performed throughout the study if clinically indicated. Perform the ECGs prior to study drug administration for all pre-dose assessments, as outlined in [Table 2-2](#). If

blood sampling or vital sign measurement is scheduled for the same visit as an ECG recording, the procedures should be performed in the following order: ECG, vital signs, blood draw.

ECG parameters to be evaluated include heart rate, PR interval, QT interval, QRS duration, and QTcF (Fridericia's correction):

$$QTcF = QT / (RR)^{0.33}$$

The ECG will be interpreted by the Investigator as normal, not clinically significant abnormal, or clinically significant abnormal. If the mean QTcF is prolonged (i.e. >500 msec, or CTCAE Grade 3) or if the mean change from baseline (value obtained at screening) is  $\geq 60$  msec, the ECGs should be reevaluated by a qualified person. Abnormalities in the ECG that lead to a change in subject management (e.g. dose reduction, interruption, treatment discontinuation, requirement for additional medication or monitoring) or results in clinical signs and symptoms that are considered clinically significant will be deemed AEs or SAEs if serious criteria are met (see Section 10.3.5).

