### 7.1.2 *Summarization by Visit*

Data summarized by study visit will be based on the nominal, scheduled visit label as reported on the eCRF. Data will also be summarized separately for the last visit completed on study.

Data collected at unscheduled visits will not be included in by-visit summaries, but will be considered when endpoint derivations potentially include multiple visits (eg, determination of baseline value, determination of worst post-baseline value, etc.). All data will be included in subject listings.

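### The QTcF threshold table is by routine visit only, so it omits unscheduled ECGs and never counts how many subjects exceeded 450, 480 or 500 msec at any time

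*SAP*

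**What the plan says.** SAP 7.5.5.2 plans three kinds of ECG summary besides descriptive statistics.

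- QTcF above 450, 480 and 500 msec is tabulated "at each visit where ECG is routinely collected per the clinical study protocol".
- Average change from baseline above 30 or 60 msec is tabulated, with no visit limit stated.
- The investigator's overall ECG reading (normal, abnormal not clinically significant, abnormal clinically significant) is cross-tabulated from baseline to the worst post-baseline value.

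SAP 7.1.2 sets the general rule for by-visit tables: "Data collected at unscheduled visits will not be included in by-visit summaries". The same section says that such data "will be considered when endpoint derivations potentially include multiple visits", and gives the worst post-baseline value as an example. It adds "All data will be included in subject listings" and "Data will also be summarized separately for the last visit completed on study".

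Protocol Table 2-2 lists routine triplicate ECGs at Screening, Cycle 1 Days 1 and 8 (before dosing and again within half an hour of the start of injection), Cycle 2 Day 1 and Cycle 3 Day 1 (both before dosing), and End of Treatment (EOT). Its last row is labelled Unscheduled: "Anytime if clinically indicated". Protocol 10.3.4 likewise provides that "Additional ECGs may also be performed throughout the study if clinically indicated". The schedule in SAP Appendix A shows the same routine ECG visits.

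**The concern.** A QTcF threshold table is normally read to learn how many subjects had a prolonged interval at any time on treatment. The planned table does not answer that, for two reasons.

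First, its visit restriction combines with an ECG schedule that stops early. After Cycle 3 Day 1, any ECG taken on treatment can only be unscheduled, so it falls outside the table. A clinically indicated ECG taken earlier, but not recorded under a routine visit, falls outside it too.

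Second, even for routine ECGs the table gives a separate percentage at each visit, not a count of distinct subjects.

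A reader of the study report could therefore see a row of zeros above 500 msec although an unscheduled ECG showed such a value.

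**Working it through.** The documents give no figure to reproduce. The check sets the rules side by side and counts the schedule.

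**Step 1. What enters the threshold table.** The table takes routine ECG visits (SAP 7.5.5.2). Clinically indicated ECGs are classed as unscheduled (Protocol Table 2-2). Unscheduled data stay out of by-visit summaries (SAP 7.1.2). An ECG taken only because it was clinically indicated is therefore not in the table.

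**Step 2. Whether the exception in SAP 7.1.2 brings it back.** The exception covers derivations that span several visits. SAP 7.5.5.2 specifies one such derivation, the shift in investigator category, which carries no msec value. None is specified for the 450, 480 and 500 msec cut-offs, so the exception has nothing to act on there. Elsewhere the SAP does use a worst post-baseline value: laboratory range shifts and toxicity grades in SAP 7.5.4, and ECOG status in SAP 7.5.5.4.

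**Step 3. Where routine on-treatment ECGs end.** Inputs: 21-day cycles, at most 35 cycles, ADU-S100 on Days 1 and 8 (Protocol synopsis and Table 2-1).

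- Cycle 3 Day 1 = 2 × 21 + 1 = Day 43.
- Last possible ADU-S100 dose, Cycle 35 Day 8 = 34 × 21 + 8 = Day 722.
- Days after the last routine on-treatment ECG, up to that dose = 722 − 43 = 679, and 679/722 = 94%.
- ADU-S100 dosing days = 35 × 2 = 70. Up to and including Cycle 3 Day 1 there are 2 + 2 + 1 = 5, so 65 of 70 (93%) come later.
- Routine ECGs fall on 4 of the 70 dosing days, and only 2 of those include a post-dose ECG.

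These shares are maxima for a subject treated for all 35 cycles; a subject who stops sooner has a smaller share. They describe the span in which an on-treatment ECG can only be unscheduled. They do not measure how many ECGs are left out, because days without an ECG have no data to omit.

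**Step 4. Why visit percentages do not give a subject count.** If n₁, …, n_k subjects exceed a cut-off at k visits, the number who ever exceeded it lies between max(nᵢ) and the smaller of Σnᵢ and N. There are five routine visits with a post-baseline ECG: Cycle 1 Day 1 (post-dose), Cycle 1 Day 8, Cycle 2 Day 1, Cycle 3 Day 1 and EOT. As an illustration only, suppose N = 20 and one subject is over the cut-off at each of the five visits. The table then shows 1/20 = 5% five times. The number ever over could be anything from 1 (5%) to 5 (5/20 = 25%), and the table cannot tell these apart.

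**Step 5. Size of one omission.** With 20 subjects, as in the protocol, one subject is 1/20 = 5 percentage points. The documents contain no QTcF data from this trial, so the number of such subjects is unknown.

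**The case against.** The strongest reply is that the values are reported elsewhere.

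- Under Protocol 10.3.4, an ECG abnormality that alters management, or produces signs or symptoms judged clinically significant, is an adverse event. SAP 7.5.2 tabulates adverse events by grade.
- Unscheduled ECGs are listed and can enter the worst-category shift table. With about 20 subjects, the listings can be read line by line.
- Protocol 12.6 promises only clinically significant ECG changes, which the shift table can serve, and all results are descriptive.
- The expected yield is low. Protocol 5.2.1 reports a low nonclinical risk of QTc prolongation, and Protocol 5.2.2 reports no clinically relevant ECG changes in the first-in-human study and a half-life of about 10 to 23 minutes.

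All of this stands, and it limits the point to one table. It does not supply the missing count. An adverse event depends on the investigator's judgement and is coded by term, the shift table has no msec scale, and a listing is not a summary.

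A reader might also infer more than the documents support:

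- **That a symptomatic subject above 500 msec would go unseen.** The adverse event tables and listings would show that subject.
- **That 94% of ECG data are discarded.** That share reflects the sparse protocol schedule; no SAP row can recover ECGs that were never taken.
- **That no later or clinically indicated ECG can be counted anywhere.** The EOT ECG counts, a repeat recorded under a routine visit label could count, the separate last-visit summary exists, and the 30 and 60 msec change categories state no visit limit.
- **That unscheduled ECGs are the likeliest to show prolongation.** The documents do not establish this.
- **That the change category is wrong because it differs from the site rule.** Protocol 10.3.4 calls for re-evaluation when mean QTcF exceeds 500 msec "or if the mean change from baseline (value obtained at screening) is" 60 msec or more, whereas the SAP tabulates changes above 60 msec from the last pre-dose value. The protocol rule is a prompt to re-read an ECG, and a table category need not copy it. On the same values the cut-offs differ only at exactly 60 msec, and the SAP uses one baseline definition for its analyses.

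**Conclusion.** The point holds for the QTcF threshold summary and not for safety reporting as a whole. As written, the summary can understate prolongation, and it gives no number of subjects ever above a cut-off, even from routine ECGs alone. The size of any understatement cannot be computed; each omitted subject would move a percentage by 5 points out of 20.

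This rests on two readings: that SAP 7.5.5.2 and SAP 7.1.2 are applied as written, and that clinically indicated ECGs are recorded as unscheduled, as Protocol Table 2-2 labels them. No efficacy endpoint is affected. The change is worth making because the SAP already uses worst post-baseline values for laboratory results and ECOG status.

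**What to change.** In SAP 7.5.5.2, add a subject-level summary with:

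- the number and percentage of subjects whose maximum post-baseline mean QTcF is above 450, 480 and 500 msec;
- the number and percentage whose maximum change from baseline is above 30 and 60 msec.

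State that both use all post-baseline ECGs, scheduled and unscheduled, under the worst-post-baseline provision in SAP 7.1.2, and keep the SAP's existing baseline definition. The by-visit table can stay.

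The cost is a short SAP wording change and one extra derived row from data already collected. No visit, ECG or clinical rule changes.

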#### 7.5.5.3 *Physical Examination*

Results of the physical examination will be presented in subject data listings by subject and study visit.

#### 7.5.5.4 *Eastern Cooperative Oncology Group (ECOG) Scale of Performance Status*

The ECOG performance status will be summarized for all subjects combined. Descriptive statistics will be presented for observed values and changes from baseline at each visit where status was scheduled to be collected. Five-by-five contingency tables will be presented to summarize the shift from the baseline category to the worst post-baseline value. Summary results will include the count and percentage of subjects within each shift category.

#### 7.5.5.5 *Prior and Concomitant Medications*

Medications will be coded using the World Health Organization Drug Dictionary Enhanced (WHODDE) Global B3, March 1, 2019. Medications entered on the eCRF will be mapped to Anatomic Therapeutic Chemical (ATC) drug class (level 4) and drug name.

Prior and concomitant medications will be summarized separately and the study phase of each medication will be determined programmatically based on medication start and end dates. A prior medication is defined as any medication used within 28 days prior to the first dose of ADU-S100. A concomitant medication is defined as any medication administered from Cycle 1 Day 1 until the EOT visit. A medication may be defined as both prior and concomitant. If it cannot be determined whether a medication was received prior to the start of study drug dosing due to partial or missing medication start and/or end dates, it will be considered a prior medication. Likewise, if it cannot be determined whether a medication was received after the start of study drug dosing, it will be considered concomitant.

For both prior and concomitant medications summaries, the number and percentage of subjects receiving any medication by ATC drug class and generic drug name will be summarized. Prior and concomitant medications will also be summarized over all subjects combined. Subjects reporting use of more than one medication at each level of summarization (any medication received, ATC class, and generic drug name) will be counted only once. ATC class terms will be displayed by descending order of incidence,

as will generic drug names within each ATC class. The study phase during which each medication was received (eg, prior, concomitant, or both) will be presented on the listing of prior and concomitant medications.

### **7.5.6 Exploratory Safety Endpoint Analysis Methods**

All exploratory endpoint laboratory data will be presented in by-subject data listings.

## **7.6 Changes in the Conduct of the Study or Planned Analyses**

Section 12.3 (“Analysis Sets”) of the protocol states the following:

*Evaluable Analysis Set (EAS): All subjects who received any amount of study drug and have at least one evaluable response assessment or were discontinued due to toxicity. The EAS will be used for analysis of the primary efficacy endpoint and clinical activity.*

- The EAS will also include subjects who died or discontinued due to clinical progression or toxicity.
- The All Treated Population will be used for analysis of the primary efficacy endpoint and clinical activity. The All Treated Population is identical to the Safety Population that is described in the protocol.
- For RECIST response SD in the calculation of DODC, duration of SD is calculated from date of baseline tumor assessment to the time of disease progression or death due to any cause. The protocol specifies to calculate this duration “from the first tumor assessment that supports the subject’s disease control” for all associated RECIST responses. This SAP further clarifies that the baseline tumor assessment can be taken as the date “supporting” the period of stable disease.

## APPENDIX A: SCHEDULE OF EVENTS

**Table 2-1 Schedule of Events**

Study Period	Screening	Treatment Period						EOT 	Follow Up 
		Cycle 1			Cycle 2 and Beyond				
Cycle Day (21-day cycles) 	-28 to -1	1	2	8	1	8	30 d post last dose	Q8W after EOT visit	
Visit Window (days)	-	-	-	±1	±1 (±3 Cycles 3-7; ±5 Cycles 8+)	±1 (±3 Cycles 3-7; ±5 Cycles 8+)	+7	+7	
Informed consent	X								
Demographics, Medical history, Height 	X								
Inclusion/Exclusion criteria	X								
SAFETY & EFFICACY EVALUATIONS									
Tumor imaging & response assessment 	X				Cycle 4 Day 1 (-7 days), Q9W (-14 days) thereafter 				
Photography of injected lesions		(pre-dose)			(pre-dose)		X		
Vital status (survival), Current cancer therapy							X	X	
ECOG performance status	X	X			X		X		
Vital signs 	X	X	X	X	X	X	X		
Physical examination, Weight 	X	X			X		X		
Electrocardiogram 	X	X		X	Cycles 2-3		X		
Adverse events 	X	X	X	X	X	X	X	X	
Prior and Concomitant medications	X	X	X	X	X	X	X	X 	
LABORATORY ASSESSMENTS (obtain prior to dosing unless otherwise indicated)									
Virology, Serology 	X								
Urinalysis, Coagulation panel 	X				As clinically indicated				
Hematology, Chemistry 	X	X 		X	X 		X		
Thyroid function 	X	X 			odd cycles 		X		
Pregnancy (WOCBP) 	Serum	Serum			X		X		
Plasma cytokines (safety) 	X	As clinically indicated for CRS initial diagnosis & follow up monitoring							
ADU-S100 PK (plasma) 		X		X	Cycle 2				
Plasma cytokines (research) 	X	X	X	X 	X 		X 	if at site 	
Whole blood (PGx) 		X							
Whole blood (transcriptomics) 	X	X	X	X	X 		X 	if at site 	
Whole blood (PBMC; select sites only) 	X	X	X	X	Cycles 2-3		X 	if at site 	
Tumor tissue (lesion for injection) 	X			X			C2D15 (±3)	Optional 	
Tumor tissue (non-injected lesion) 	X						C2D15 (±3)	Optional 	
STUDY DRUG ADMINISTRATION									
Pembrolizumab (IV infusion) 		X			X				
ADU-S100 (intratumoral injection) 		X 		X	X	X			

